4.4.6 Left Ventricular Ejection Fraction

All patients will require evaluation of LVEF at screening and Cohorts A and B will require subsequent evaluations of LVEF.

Evaluation of LVEF by ECHO or MUGA scan must be performed at the following timepoints:

- Screening
- Cycle 2, Day 1 \pm 1 week
- Day 1 of every three treatment cycles thereafter, starting at Cycle 5 (\pm 2 weeks)
- The treatment discontinuation visit evaluation of LVEF does not need to be performed at the treatment discontinuation visit if an evaluation has been performed within the last 12 weeks, and there are no clinically significant findings and/or changes from baseline.
- All patients restarting treatment with a dose reduction of cobimetinib because of a decrease in LVEF should have LVEF measurements taken after approximately 2, 4, 10, and 16 weeks, and then resume monitoring LVEF every three treatment cycles.

Any patient who develops clinical signs or symptoms suspicious of cardiac failure should undergo an LVEF assessment. Evaluation of LVEF must be performed by the same method (ECHO or MUGA scan) for each patient. It is strongly encouraged that the same laboratory and operator perform ECHO/MUGA scans for each patient. Investigators

must be aware of local institution regulations regarding repeat MUGA scans. The repeat administration of radioisotopes is limited in some nuclear medicine laboratories, and some patients in this study could require monitoring on four or more occasions.

4.4.7 Ophthalmologic Examination (Cohorts A and B)

All patients in Cohorts A and B will require an ophthalmologic examination at screening and subsequent ophthalmologic examinations. The objective of a baseline ophthalmologic examination is to evaluate for evidence of retinal abnormalities. An ophthalmologic examination must be performed by a qualified ophthalmologist.

Baseline and serial surveillance ophthalmologic examinations will include visual acuity testing using a standard Snellen chart, intraocular pressure measurement by tonometry, slit-lamp biomicroscopy, indirect ophthalmoscopy, spectral-domain optical coherence tomography (OCT), and automatic visual field testing. Spectral-domain OCT, if not available, may be substituted with time-domain OCT. Ophthalmologic examinations must be performed according to the schedule in [Table 3](#).

Table 3 Ophthalmologic Examination Schedule

	Frequency	Assessments
Screening	One time	Visual acuity test, VF 24-2, slit-lamp biomicroscopy, IOP measurement, OCT, indirect ophthalmoscopy
Cycles 1 and 2	Q2W (± 1) day of the scheduled visit, if serous retinopathy is not detected	Visual acuity test, OCT, indirect ophthalmoscopy ^a
	Increase to QW (± 1) day, if serous retinopathy is detected, until resolution or until Cycle 2, Day 28, whichever occurs first	Visual acuity test, VF ^b , OCT, indirect ophthalmoscopy
Cycles 3 to 6	Q4W ± 1 day of the scheduled visit, if serous retinopathy is not diagnosed	Visual acuity test, OCT, indirect ophthalmoscopy ^a
	Increase to Q2W ± 1 day, if serous retinopathy is detected, until resolution or until Cycle 6, Day 28, whichever occurs first	Visual acuity test, VF ^b , OCT, indirect ophthalmoscopy

Table 3 Ophthalmologic Examination Schedule (cont.)

From Cycle 7	Every 3 cycles (± 2 weeks)	Visual acuity test, indirect ophthalmoscopy ^c
Treatment discontinuation ^d	One time	Visual acuity test, VF ^b , slit-lamp biomicroscopy, IOP measurement, OCT, indirect ophthalmoscopy

IOP=intraocular pressure; OCT=optical coherence tomography; Q2W = every two weeks; Q4W = every 4 weeks; VF=visual field.

Note: Examinations should be performed prior to dosing.

^a If serous retinopathy is diagnosed at any visit, patients must also have visual field testing if not already performed at this visit.

^b Perform Swedish Interactive Threshold Algorithm Fast strategy (or equivalent):

- 10-2 threshold test if serous retinopathy is detected only within the macula
- 24-2 threshold test if serous retinopathy is extramacular or if extends beyond the macula

^c Per ophthalmologist discretion, may perform other clinically indicated tests. Also refer to management guidelines in [Table 6](#).

^d Does not need to be performed if an evaluation has been performed within the last 12 weeks and no signs of serous retinopathy were detected.

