
 To evaluate the efficacy of cobimetinib and atezolizumab in patients with advanced BRAF^{V600} WT melanoma who have progressed on prior anti-PD-1 therapy To evaluate the efficacy of atezolizumab monotherapy in patients with advanced BRAF^{V600} WT melanoma who have not been previously treated 	
 ORR as determined by the investigator according to immune-modified RECIST DOR as determined by the investigator according to immune-modified RECIST PFS as determined by the investigator according to immune-modified RECIST
Safety Objectives	

 To evaluate the safety of cobimetinib and atezolizumab in patients with advanced BRAF^{V600} WT melanoma who have progressed on prior anti-PD-1 therapy To evaluate the safety of atezolizumab monotherapy in patients with advanced BRAF^{V600} WT melanoma who have not been previously treated 	
 Occurrence, frequency, and severity of adverse events, with severity determined through use of NCI CTCAE v4.0 Change from baseline in targeted vital signs during and following treatment Change from baseline in targeted clinical laboratory test results during and following treatment Incidence, severity and time course of serous retinopathy (for Cohorts A and B)

Table 1 Objectives and Corresponding Endpoints (cont.)

Pharmacokinetic Objectives	

 To characterize the pharmacokinetics of atezolizumab monotherapy in Cohort C To characterize the pharmacokinetics of cobimetinib and atezolizumab when administered in combination in Cohorts A and B 	
 Serum concentration of atezolizumab at specified timepoints Plasma concentration of cobimetinib at specified timepoints
Exploratory Pharmacokinetic Objectives	

 To investigate the relationship between cobimetinib exposure and efficacy or safety outcomes using population approaches To investigate the relationship between atezolizumab exposure and efficacy or safety outcomes using population approaches 	
 Relationship between cobimetinib plasma concentration and efficacy or safety endpoints Relationship between atezolizumab serum concentration and efficacy or safety endpoints
Immunogenicity Objective	

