3.3.7 Rationale for Ophthalmologic Assessments (Cohorts A and B)

Serous retinopathy has been observed in patients treated with MEK-inhibitors, including cobimetinib (Flaherty et al. 2012). Manifestations of serous retinopathy include retinal detachment (i.e., fluid accumulation between the neurosensory retina and the retinal pigment epithelium) and retinopathy. Although serous retinopathy can lead to visual disturbances, in some circumstances it may also be asymptomatic.

Serous retinopathy was prospectively monitored in Study GO28141 in all patients. Serous retinopathy was reported more frequently in patients treated with cobimetinib plus vemurafenib than placebo plus vemurafenib (25.5% vs. 2.8%, respectively), and approximately half the events were asymptomatic Grade 1 events. Few patients treated with cobimetinib plus vemurafenib experienced Grade ≥ 3 ocular events (2.8%); the majority of these events were managed with dose modification of both cobimetinib and vemurafenib. Most events of serous retinopathy occurred early in treatment with a median onset of 1 month (De la Cruz-Merino et al. 2015).

In order to further characterize the nature and time course of this adverse event, and its impact to patients, additional ophthalmologic investigations have been incorporated in this study. All patients are required to undergo a baseline ophthalmologic examination to assess for history or evidence of retinal abnormalities. Thereafter, patients will have comprehensive ophthalmologic testing every 2 weeks during the first two cycles of treatment, and then every 4 weeks until Day 1 of Cycle 7 (Cohorts A and B). If serous retinopathy is detected at any of these visits, monitoring will be continued at increased frequency (see Section 4.4.7) until the adverse event resolves or 6 months have elapsed, whichever occurs first.

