Serous retinopathy Severity grade assessment based on NCI CTCAE v4.0 "Eye Disorders-Other" scale ^{a, b, c, d}	
Serous retinopathy, Grade 1^a or 2^b (tolerable):
 
 • Continue cobimetinib and atezolizumab without dose change. • Follow the monitoring schedule detailed in Section 4.4.7. 
Serous retinopathy, Grade 2^b (intolerable) or Grade 3 or 4:^{c, d}
 
 • Interrupt cobimetinib until Grade ≤ 1. • Continue atezolizumab as clinically indicated. • Consult ophthalmology and undergo complete ophthalmologic examination, which includes visual acuity testing, intra-ocular pressure measurements, slit lamp ophthalmoscopy, indirect ophthalmoscopy, visual field, and OCT. Consider a fluorescein angiogram and/or indocyanine green angiogram, if clinically indicated. • Follow the monitoring schedule detailed in Section 4.4.7. • The dose of cobimetinib should be reduced by one dose level when restarting. • Consider permanent discontinuation of cobimetinib if serous retinopathy recurs despite two dose level reductions.

ADL = activities of daily living; NCI CTCAE v4.0 = National Cancer Institute Common Terminology Criteria for Adverse Events, Version 4.0; OCT = optical coherence tomography; RVO = retinal vein occlusion.

^a Grade 1: Asymptomatic or mild symptoms; clinical or diagnostic observations only; intervention not indicated.

^b Grade 2: Moderate; minimal, local or noninvasive intervention indicated; limiting age appropriate instrumental ADL.

^c Grade 3: Severe or medically significant but not immediately sight threatening; hospitalization or prolongation of existing hospitalization indicated; disabling; limiting self-care ADL.

^d Grade 4: Sight-threatening consequences; urgent intervention indicated; blindness (20/200 or worse) in the affected eye.

Table 6 Guidelines for Management of Patients Who Experience Specific Adverse Events (Cobimetinib and Atezolizumab) (cont.)

Event	Action to Be Taken
Ocular toxicity (cont.)	
Potential immune-related ocular toxicity (e.g., uveitis, iritis, episcleritis, or retinitis)	
 • Follow guidelines provided in Appendix 8. • Continue cobimetinib as clinically indicated.
RVO (any grade)	
 • If RVO (any grade) is diagnosed, cobimetinib dosing should be permanently discontinued and RVO treated per institutional guidelines. • Continue atezolizumab.

RVO = retinal vein occlusion.

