6.5 SAFETY ANALYSES

The safety analyses will include all patients who receive at least one dose of study drug.

Safety will be assessed through summaries of adverse events, changes in laboratory test results, changes in vital signs, and study treatment exposure.

Verbatim description of adverse events will be summarized by mapped terms and appropriate thesaurus levels and graded according to NCI CTCAE v4.0. All adverse events that occur during or after the first study drug dose will be summarized by NCI CTCAE grade. In addition, serious adverse events, severe adverse events (Grades ≥ 3), adverse events of special interest, and adverse events leading to study drug discontinuation or interruption will be summarized accordingly. Multiple occurrences of the same event will be counted once at the maximum severity. The proportion of patients who experience at least one adverse event will be reported by toxicity term.

Study drug exposure, including treatment duration, number of doses, and dose intensity, will be summarized using descriptive statistics.

All deaths and causes of death will be summarized.

Laboratory data with values outside the normal ranges will be identified. In addition, relevant laboratory data and vital signs will be summarized.

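### Table 6 both withholds and continues cobimetinib for tolerable Grade 2 serous retinopathy; a minor second mismatch is when increased eye monitoring ends

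*Combined protocol and SAP*

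**What the plan says.** **Dosing.** Section 5.1.1.1.2 sends sites to Section 5.1.3.3 for retinopathy of Grade 2 or higher. There, three texts apply:

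- Table 6, ocular toxicity, general guidance: once serous retinopathy is diagnosed, cobimetinib is to be held until visual symptoms are Grade 1 or lower. The sentence has no exception by grade or tolerability.
- Table 6, serous retinopathy row: for Grade 1 or tolerable Grade 2, both drugs continue unchanged. For intolerable Grade 2, or Grade 3 or 4, cobimetinib is interrupted until Grade 1 or lower and restarted one dose level down.
- Table 5 (all toxicities): Grade 1 or tolerable Grade 2 stays at 60 mg. Intolerable Grade 2, or Grade 3 or 4, is interrupted and restarted at 40 mg on first appearance.

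**Monitoring.** In Cycles 3 to 6, Table 3 in Section 4.4.7 raises examinations to every 2 weeks "if serous retinopathy is detected, until resolution or until Cycle 6, Day 28, whichever occurs first". From Cycle 7 it asks for "Visual acuity test, indirect ophthalmoscopy" every 3 cycles, and its footnote adds: "Per ophthalmologist discretion, may perform other clinically indicated tests". Section 3.3.7 says that, for an event detected at a scheduled visit, "monitoring will be continued at increased frequency (see Section 4.4.7) until the adverse event resolves or 6 months have elapsed, whichever occurs first". It does not say when the 6 months begin.

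**Endpoint and analysis.** Table 1 in Section 2 makes the time course of serous retinopathy, alongside its incidence and severity, a safety endpoint for Cohorts A and B. Section 6.5 states: "Safety will be assessed through summaries of adverse events, changes in laboratory test results, changes in vital signs, and study treatment exposure". It also summarises adverse events of special interest, and Section 5.2.3 lists serous retinopathy among these. It does not mention the eye examinations or a time-course summary.

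**The concern.** A patient with tolerable Grade 2 serous retinopathy fits both Table 6 instructions, and they lead to different treatment. One site keeps the patient on 60 mg. Another stops the drug. The withholding sentence gives no restart dose, so the second site may borrow the one-level reduction from the intolerable row. It also meets the general Table 6 rule under which a hold of more than 28 days for toxicity leads to discontinuation unless the Medical Monitor approves resumption. Patients with the same grade of a known cobimetinib toxicity could therefore receive different exposure for no planned reason, and times to resolution on and off drug would be mixed in the one endpoint meant to describe the course of this event.

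The monitoring mismatch is smaller. Section 3.3.7 notes that in GO28141 "approximately half the events were asymptomatic Grade 1 events". For such events clearing is seen only at an examination, so the examination interval limits how precisely resolution can be dated. Section 3.3.7 and Table 3 disagree on when the short interval ends.

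**Working it through.** **1. Which events meet the dosing conflict.** Set the instructions side by side by grade:

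| Event | General guidance | Serous retinopathy row | Table 5 | Conflict |
|---|---|---|---|---|
| Grade 1 | Hold until symptoms Grade 1 or lower: already met | Continue | Continue | None in practice |
| Grade 2, tolerable | Hold | Continue | Continue | Yes |
| Grade 2, intolerable | Hold | Interrupt, reduce | Interrupt, reduce | None |
| Grade 3 or 4 | Hold | Interrupt, reduce | Interrupt, reduce | None |

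Only one cell conflicts. There, the patient either stays on 60 mg or is held and possibly restarted at 40 mg, a daily dose lower by 20/60 = one third.

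**2. How many patients.** The documents give no rate for this combination. As an assumption, take the GO28141 rates in Section 3.3.7 (cobimetinib plus vemurafenib) and the 102 patients of Cohorts A and B:

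- Cases: 0.255 × 102 = 26.0.
- Beyond asymptomatic Grade 1: about half, 13.0.
- Grade 3 or higher: 0.028 × 102 = 2.9. This figure covers all ocular events, so between 0 and 2.9 are serous retinopathy.
- Left for Grade 2: 13.0 − 2.9 = 10.1 up to 13.0, fewer if some symptomatic events were still Grade 1.

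The share that is tolerable is not given. Over its full range, 0 to about 13 patients would meet the conflict.

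**3. Size of the monitoring mismatch.** Cycles are 28 days, so Cycle 6 Day 28 = 6 × 28 = day 168 if no cycle is delayed.

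- 6 months from first dose: 24 weeks = 168 days gives a gap of 0; calendar months, 183 days, give 183 − 168 = 15 days, about one 2-weekly examination.
- 6 months from detection on day *d*: gap = *d* + 183 − 168 = *d* + 15. Day 29 gives 44 days; Cycle 6 Day 1 (day 141) gives 156 days.
- An event found at Cycle 7 Day 1 (day 169) would get 183 days of increased monitoring if counted from detection, at most about two weeks if counted from first dose, and none under Table 3.

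**4. What the mismatch changes.** Only events still open at, or found at, Cycle 7 Day 1 are affected. If clearing is uniform between examinations and no extra examination is done, it is dated on average 14/2 = 7 days late with 2-weekly examinations and 84/2 = 42 days late with examinations every 3 cycles (3 × 28 = 84 days). The documents do not give the share of events open at day 168. At an assumed 5% to 40% of 26 cases, that is 1.3 to 10.4 patients.

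**The case against.** **On dosing.** A specific row is normally read as overriding general guidance, and the sentence after the withholding instruction treats interruption as one of several options. Many investigators would reach the intended answer. This has force, and Table 5 makes the intention fairly clear. But the protocol states no order of precedence, and the withholding sentence applies from diagnosis without exception. A site following it literally would depart from the row just below.

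**On monitoring.** A reader might infer that sites face two rival stopping rules, so that recorded duration depends on which one they choose and can differ by months. The documents do not support this. The Section 3.3.7 sentence itself refers to Section 4.4.7. Section 4.4.7 makes Table 3 mandatory. Table 6 says "Follow the monitoring schedule detailed in Section 4.4.7", and the Appendix 1 schedules for Cohorts A and B point there too. The gaps of 44 to 156 days also require the 6 months to run from detection, which is not stated.

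Nor does recording stop at day 168. Section 5.5.1 follows each event until it resolves or is judged stable, with resolution dates on the eCRF. Table 6 calls for a complete eye examination, including OCT, for intolerable Grade 2 or Grade 3 or 4 events at any cycle, and unplanned visits are allowed. The 42-day figure is therefore nearer a worst case.

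**On analysis.** A reader might also infer that the time-course endpoint cannot be reported. It can, descriptively, from special-interest event records and resolution dates. What remains is that Section 6.5 does not say how.

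**Conclusion.** The dosing contradiction is real and stands on the text alone: for tolerable Grade 2 serous retinopathy, Table 6 cannot be followed as written. It should be corrected because it governs treatment for a monitored toxicity. The count of 0 to about 13 patients rests on rates from a vemurafenib combination, which may not carry over, and on an undocumented tolerable share. The case for correction does not depend on that count.

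The end-of-monitoring mismatch is a minor wording inconsistency. Table 3 is the working rule, and the effect is confined to how precisely resolution is dated for a few late or persistent events. Treatment delays would move Cycle 6 Day 28 later and narrow the gap. The documents do not show that extra examinations after Cycle 6 are needed.

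Neither point changes the definition or analysis of incidence, severity or the co-primary endpoints (ORR and DCR).

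**What to change.** 1. **Table 6, ocular general guidance.** Limit the withholding sentence to intolerable Grade 2 and Grade 3 or 4 serous retinopathy, and refer to the row below for Grade 1 and tolerable Grade 2. This matches both the row and Table 5. If the sponsor instead wants every Grade 2 event held, the serous retinopathy row must change, with a restart dose stated and an exception to Table 5.
2. **Section 3.3.7.** Replace the 6-month limit with the Table 3 limit: resolution or Cycle 6 Day 28, then every 3 cycles.
3. **Optional, Section 6.5.** Add one sentence: for Cohorts A and B, describe time from first cobimetinib dose to detection and time to resolution from the Section 4.4.7 examinations, with resolution shown as the interval between last abnormal and first clear examination, unresolved events shown as ongoing at the last examination, and cobimetinib marked as held or continued.

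The cost is two sentences of protocol text, which can go into the next amendment. The optional item adds one descriptive table from event, dosing and eye-examination data already collected. No examination, visit or patient is added.

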4.5 PATIENT, TREATMENT, STUDY, AND SITE DISCONTINUATION

4.5.1 Patient Discontinuation

Patients have the right to voluntarily withdraw from the study at any time for any reason. In addition, the investigator has the right to withdraw a patient from the study at any time. Reasons for withdrawal from the study may include, but are not limited to, the following:

- Patient withdrawal of consent at any time
- Any medical condition that the investigator or Sponsor determines may jeopardize the patient's safety if he or she continues in the study
- Investigator or Sponsor determines it is in the best interest of the patient
- Patient non-compliance, defined as failure to comply with protocol requirements as determined by the investigator or Sponsor

Every effort should be made to obtain information on patients who withdraw from the study. The primary reason for withdrawal from the study should be documented on the appropriate eCRF. However, patients will not be followed for any reason after consent has been withdrawn. Patients who withdraw from the study will not be replaced.

4.5.2 Laboratory, Biomarker, and Other Biologic Samples

4.5.2.1 Local Laboratory Assessments

Samples for the following laboratory tests will be sent to the study site's local laboratory for analysis:

- Hematology: WBC count, RBC count, hemoglobin, hematocrit, platelet count, reticulocyte count, and differential count (neutrophils, bands, eosinophils, basophils, monocytes, and lymphocytes)
- Chemistry panel (serum or plasma): sodium, potassium, magnesium, chloride, bicarbonate (or total carbon dioxide), BUN or urea, creatinine, albumin, phosphorus, calcium, direct and total bilirubin, ALP, ALT, AST, LDH, CPK, and glucose (non-fasting), total protein, and uric acid
- Fasting blood glucose (after a minimum 8-hour fast), at screening only
- Fasting lipids: total cholesterol, LDL cholesterol, and triglycerides (after a minimum 8-hour fast), at screening only
- Coagulation: INR, aPTT
- Thyroid-function testing: thyroid-stimulating hormone, free triiodothyronine (T3; or total T3 for sites where free T3 is not performed), and free thyroxine
- Urinalysis (specific gravity, pH, glucose, protein, ketones, blood and microscopic examination)
- HIV serology
- HBV serology: HBsAg, and total HBcAb and (if HBsAg test is negative and total HBcAb test is positive) HBV DNA

If a patient has a negative HBsAg test and a positive total HBcAb test at screening, an HBV DNA test must also be performed to determine if the patient has an HBV infection.

- HCV serology: HCV antibody and (if HCV antibody test is positive) HCV RNA

If a patient has a positive HCV antibody test at screening, an HCV RNA test must also be performed to determine if the patient has an active HCV infection.

- Pregnancy test

All women of childbearing potential will have a serum pregnancy test at screening, within 7 days before initiation of study treatment. Urine pregnancy tests will be performed at specified subsequent visits. If a urine pregnancy test is positive, it must be confirmed by a serum pregnancy test.

A woman is considered to be of childbearing potential if she is postmenarcheal, has not reached a postmenopausal state (≥ 12 continuous months of amenorrhea with no identified cause other than menopause), and has not undergone surgical sterilization (removal of ovaries and/or uterus).

